Sustaining a CUSP Team	CUSP team and all psychiatric rehabilitation program staff	60 minutes	

Data Collection:

Study data collection is outlined in Table 2 and in more detail below. Study team involvement in data collection is all virtual/remote.

Table 2. Study Data Collection			
Qualitative Data Collection	Who	Estimated time	When
CUSP Team Focus Groups	Selected CUSP team members (~5 per site)	60 minutes	Baseline, 15 months
Primary Care Provider Interviews	Primary care providers caring for health home program patients but who are not health home team members (~5 per site)	30 minutes	Baseline
Survey Measures			
Demographic Characteristics: age, sex, race, ethnicity, length of time at program, role in program, previous Motivational Interviewing training, comfort with technology	Health home team and psychiatric rehabilitation program staff (~30 per site)	~5 minutes	Baseline
Implementation Climate: This is a measure of the degree to which an organization supports evidence-based practice implementation	Health home team and psychiatric rehabilitation program staff (~30 per site)	~3 minutes	Baseline
Quality Improvement Culture: Measured using a modified version of the validated 42-item Survey on Patient safety used in inpatient CUSPs	Health home team and psychiatric rehabilitation program staff (~30 per site)	~5 minutes	Baseline, 12 months

Pre-Implementation Health Homes Survey: The nurse care manager will assess the behavioral health home's database and what is currently tracked.	CUSP team member (health home nurse/nurse care manager) (1 per site)	~10 minutes	Baseline
Self-Efficacy: Self-efficacy to deliver evidence-based CVD risk factor	CUSP team (~10 per site)	~5 minutes	Baseline, 12 months
Acceptability, Appropriateness, and Feasibility of the Intervention Implementation Strategies: Measured with a brief 4-item practice instrument (AIM, IAM, FIM) ⁶⁷	CUSP team (~10 per site)	~5 minutes	Baseline, 12 months
Acceptability, Appropriateness, and Feasibility of the Evidence-Based Practice Bundle: Measured with a brief 4-item practice instrument (AIM, IAM, FIM) ⁶⁷	CUSP team (~10 per site)	~5 minutes	Baseline, 12 months
Motivation: Degree to which providers and staff agree or disagree with statements that deal with aspects of the health homes intervention to improve cardiovascular risk factor care	CUSP team (~10 per site)	~3 minutes	Baseline, 12 months

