As part of implementing the evidence-bundle on management of CVD risk factors, care coordination and population health, CUSP team members will be using a standard population health spreadsheet template that the study team provides to track CVD risk factors and care processes during regular health home program care. Using the spreadsheet, CUSP team members can aggregate patient-level data and identify trends in CVD risk factor prevalence and quality of care metrics for persons enrolled in the health home. This data (in a limited dataset) will also be used for study evaluation purposes. Health home enrollee data will include sociodemographic and basic mental health diagnosis/medication categories, CVD risk factors, evidence-based CVD risk factor care processes and CVD risk factor control.

Data Management:

Qualitative data. Interview and focus group data will be audio or video-recorded and

recordings will be transcribed using Production Transcripts, Inc or another approved Johns Hopkins vendor. Names will be removed from transcripts. Recordings will be stored in a Johns Hopkins secure network drive and will be destroyed when analyses are complete. Standardized actor interview recordings will be reviewed by experts in motivational interviewing for fidelity to motivational interviewing practices and stored in a Johns Hopkins secure network drive or OneDrive.

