Quantitative data. Each participant will be assigned a unique study ID number for data collection. We will store data in a Johns Hopkins REDCap database. Study team members are trained to protect integrity and confidentiality of the data. Kognito, a health simulation company, developed the avatar simulations for this project and hosts the avatar training platform and dashboard. Avatar performance measurement data for motivational interviewing practice conversations is accessible only by the individual study participant (CUSP team member) and the study team, not shared outside Kognito. Kognito stores data securely behind two firewalls. For health home enrollee measures, the CUSP team will use participant initials and a study ID number in the Excel population health tracking spreadsheet. Participant names, used for implementing the evidence-bundle, will be removed by the CUSP team. They will use Johns Hopkins OneDrive, available to non-Johns Hopkins collaborators, to deposit the spreadsheet at baseline, 6 and 12 months. The data will contain no names or birthdates but will have dates of process measures (e.g., lab values) thus it will be a limited dataset. Each study site will only be able to access a folder specific to their site, and spreadsheets will have password protection.

- c. Blinding, including justification for blinding or not blinding the trial, if applicable.
N/A
- d. Justification of why participants will not receive routine care or will have current therapy stopped. N/A
- e. Justification for inclusion of a placebo or non-treatment group N/A
- f. Definition of treatment failure or participant removal criteria. N/A
- g. Description of what happens to participants receiving therapy when study ends or if a participant's participation in the study ends prematurely. N/A

5. Inclusion/Exclusion Criteria

Psychiatric rehabilitation program and health home team staff, including providers and leadership are those employed by the psychiatric rehabilitation program or health home program. All are adults and English-speaking.

Primary care providers are those who provide primary care to health home enrollees.

Health home enrollees are by definition persons with serious mental illness who are members of a behavioral health home. All are 18 years and older.

6. Drugs/ Substances/ Devices-N/A

- a. The rationale for choosing the drug and dose or for choosing the device to be used.

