- b. Justification and safety information if FDA approved drugs will be administered for non-FDA approved indications or if doses or routes of administration or participant populations are changed.

- c. Justification and safety information if non-FDA approved drugs without an IND will be administered.

7. Study Statistics

- a. Primary outcome variable and analytic plans

We will conduct three main analyses. First, we will compare pre/post (baseline, 12 mo.) quality improvement culture and provider self-efficacy, the mechanisms through which CUSP is designed to improve delivery of evidence-based care, using a generalized linear mixed effects modeling approach. We will evaluate the effects of CUSP (baseline, 6 mo, 12 mo) on consumer-level evidence-based care and CVD risk factor control outcomes using a multi-level modeling approach. We will assess mediator and moderator by testing whether sites' quality improvement culture and provider self-efficacy mediate CUSP's effects on health home enrollee outcomes by adding these variables to the multi-level models of health home enrollee outcomes. We will also assess potential moderating effects of implementation climate by adding appropriate interaction terms to the main models. We will use descriptive statistics to analyze survey measures of staff perceptions of the acceptability, feasibility and appropriateness of CUSP and the evidence-bundle. Interview and focus group transcripts will be analyzed in NVivo V.11, using inductive coding to identify key themes. Survey analysis will be done using Stata 14 or SAS software.

8. Risks

We expect any risk to be minimal in this study.

- a. Medical risks, listing all procedures, their major and minor risks and expected frequency.

For the CUSP implementation of the evidence-based bundle for CVD risk factor care, coordination and population health, the health home programs are already providing care in these domains for their enrollees with serious mental illness. Health home staff will be working within their current scope of practice with this project. The evidenced-based practices the study team is providing training for as part of the CUSP model are based on current practice guidelines. CUSP is a quality improvement implementation strategy. Thus, we do not expect there to be increased risk for health home enrollees.

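### Section 7 promises the effects of CUSP and their mediators, but five sites that all receive CUSP, with one wave before implementation, can show only change from baseline

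*Combined protocol and SAP*

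**What the plan says.** Section 7 describes its first analysis as a before-after comparison: "First, we will compare pre/post (baseline, 12 mo.) quality improvement culture and provider self-efficacy". For enrollee outcomes the language changes: "We will evaluate the effects of CUSP (baseline, 6 mo, 12 mo) on consumer-level evidence-based care", together with risk factor control, by multi-level modelling. Sites' culture and provider self-efficacy are then to be tested as mediators of CUSP's "effects on health home enrollee outcomes by adding these variables to the multi-level models". Last comes moderation: "We will also assess potential moderating effects of implementation climate by adding appropriate interaction terms to the main models".

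The design is set out in Section 4. Each of the five programs forms a CUSP team and implements CUSP for 12 months. Item e reads "Justification for inclusion of a placebo or non-treatment group N/A". Under Data Management, the sites "deposit the spreadsheet at baseline, 6 and 12 months". Table 2 schedules quality improvement culture and self-efficacy at baseline and 12 months, and implementation climate at baseline only. It puts enrollment at about 200 per site.

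On recording, Section 4 says that health homes already measure cardiovascular risk factor care, but not by standard processes. During the study, "CUSP team members will be using a standard population health spreadsheet template that the study team provides".

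**The concern.** An effect of CUSP is the difference between what happened with it and what would have happened without it. Nothing in the design supplies the second quantity: there is no untreated site, no staggered start and no planned pre-baseline series. Mediation needs more still, namely a mediator that is observed to move before the outcome does.

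An uncontrolled pilot is a legitimate design. What is at stake is what it hands on. The Abstract says the results will be the basis for developing and evaluating a scalable model. If Section 7 is followed literally, that later work would receive change from baseline labelled as an effect, and associations across five sites labelled as a mechanism.

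**Working it through.** The documents give no sample size calculation, effect size, SD or intraclass correlation, so there is no planned figure to reproduce. Steps 1 to 3 use only the documents' facts. Step 4 uses assumed SDs.

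**1. Can a CUSP effect be separated from time?** Inputs: 5 sites; waves at 0, 6 and 12 months; CUSP = 0 at baseline and 1 at both later waves, because implementation lasts 12 months.
- Columns: intercept (1) + sites (4) + 6-month and 12-month indicators (2) + CUSP (1) = 8. Rank = 7.
- The deficiency is exact: CUSP = 6-month indicator + 12-month indicator.
- Put another way, change at wave t is trend(t) + CUSP effect(t), and only the sum is estimable. Any background change enters the estimate point for point. The documents give neither its size nor its direction.
- Replacing the wave indicators by a straight line restores full rank (7 of 7), but the CUSP step then becomes 2·y6 − y0 − y12. That treats the 6-to-12-month slope, which is itself under CUSP, as the background trend.

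**2. Mediator timing (Table 2).**

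| Wave | Enrollee outcome | Culture, self-efficacy |
|---|---|---|
| Baseline | yes | yes |
| 6 months | yes | no |
| 12 months | yes | yes |

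Only 2 of the 3 waves have both. The second mediator reading comes after the 6-month outcome and at the same time as the 12-month outcome, so temporal order is never observed. As site characteristics, the mediators give five changes each. Regressing five site changes on one covariate leaves 5 − 2 = 3 degrees of freedom. The critical t is 3.182, so significance needs |r| ≥ 3.182/√(3 + 3.182²) = 0.878.

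**3. Moderation by climate.** Let the change at site s be d + g·c_s, where c_s is baseline climate. A trend common to all sites goes into d and cancels from the slope g. If the trend itself varies with climate, as d + h·c_s, the slope becomes g + h, and the two parts cannot be separated. The slope also rests on five values of c_s.

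**4. Inference for site-level covariates.** Suppose the model has only site and enrollee random intercepts, and the covariate has no true association with change. With n enrollees per site, enrollee change SD 0.5 (assumed) and site-change SD σ (assumed), a nominal 5% enrollee-level test rejects with probability

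2·[1 − Φ(1.96/√(1 + n·σ²/0.25))].

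| σ | n = 50 | n = 100 | n = 200 |
|---|---|---|---|
| 0 | 5% | 5% | 5% |
| 0.02 | 6% | 7% | 9% |
| 0.04 | 9% | 13% | 19% |
| 0.08 | 19% | 30% | 43% |

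Example: σ = 0.04, n = 200 gives √(1 + 200 × 0.0016/0.25) = √2.28 = 1.510; 1.96/1.510 = 1.298; two-sided 19%. Simulation agrees with the table to within one percentage point. A three-wave random-intercept model, with its variances also assumed, gave 9.2%, 13.6% and 19.7% at σ = 0.04.

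Two remedies were simulated under the same assumptions. A t test on the five site values (3 df) held 5% in every cell. A site-by-time random effect fitted by REML with a Wald z test rejected 6%, 7% and 10% at σ = 0.04, and 10% to 13% at σ = 0.08.

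**The case against.** The strongest reply is that this is a pilot. Aim 2 promises only preliminary data on enrollee outcomes, Section 7 calls its first analysis pre/post, and evaluation of a scalable model is left to later work. That is a fair defence of the design, and the design and the Aim 2 hypotheses can stand. But calling data preliminary says they are imprecise or not final. It does not say that change cannot be attributed to CUSP, and no passage does.

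It can also be said that Section 7 never writes a CUSP indicator next to saturated time, so the rank result describes a model that nobody proposed. That is correct: it is not a coding error in the plan. It is a compact proof that no model of these data yields a CUSP effect without an assumption about trend, and none is stated.

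Three stronger readings are tempting, and the documents do not support them.
- *Recording changed between baseline and follow-up.* Standard tracking does arrive with CUSP, so completeness could improve. But the same spreadsheet is deposited at all three waves, Aim 1 lists database abstraction among its methods, and the nurse care manager assesses existing tracking at baseline. The Background statement that tracking systems are lacking comes from earlier research on health homes in general. Changed ascertainment is a risk, not an established fact.
- *Moderation is as confounded as the main change.* It is not, because a common trend cancels (step 3).
- *The planned tests will have inflated error.* Section 7 does not specify the random effects. The rates in step 4 apply only if site-by-time variation is left out. They depend on assumed SDs, use a linear outcome where the plan's outcomes are percentages, and show no inflation at σ = 0.

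**Conclusion.** Section 7 is wrong as written in what it says will be estimated. Unless one assumes no secular trend, the models give change from baseline. This follows from the documents' own facts, and more enrollees would not alter it. Mediation cannot be established, because the mediators have no 6-month value, their second reading coincides with the final outcome, and they supply five site values each. Climate moderation is less exposed, but it rests on five values and cannot be read as moderation of a CUSP effect if trends differ with climate.

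The testing problem is conditional. If site-by-time variation is omitted, a nominal 5% test rejects about 9% to 20% of the time at an assumed site-change SD of 0.04 with 50 to 200 enrollees per site, more at larger SDs, and 5% at SD 0. The first two conclusions do not depend on these figures. The fault lies in the claims and the inference in Section 7, not in the choice of a single-arm pilot.

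**What to change.** In Section 7:

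(a) In the sentence on enrollee outcomes, replace the promise to evaluate CUSP's effects with: *estimate change from baseline to 6 and 12 months in*.

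(b) Recast mediation and implementation-climate moderation as exploratory site-level associations with change in enrollee outcomes. State that mediator models use the baseline and 12-month waves. Base inference on the five sites, through site-level estimates with t intervals on 3 degrees of freedom, taking one covariate at a time. If a site-by-time random effect is preferred, pair it with a small-sample degrees-of-freedom correction, because a Wald z test does not reliably control error with five sites.

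(c) Add: *Without a comparator, the observed changes are preliminary and cannot be separated from secular trend or changed ascertainment.*

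This needs no new data, sites or time. Items (a) and (c) are wording, and (b) is a site-level summary or one model term with a correction. The price is a less favourable claim and wide intervals, so the mediation and moderation results will be largely descriptive.

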Health homes are currently implemented in 48 Maryland psychiatric rehabilitation programs, which receive a per-member-per-month payment to provide “health home services,” including primary care coordination and case management.⁵⁵ All health homes have a director, primary care physician or nurse practitioner consultant, and one or more nurse care managers, but each site chooses their own service structure (ranging from co-location to facilitated referral to offsite primary care services).⁵⁵ Nurse care managers provide basic services, like blood pressure monitoring, onsite.³⁴ While 15% of sites have a primary care provider who provides onsite services 1+ days per week, most primary care physical health services are coordinated with offsite providers.³⁴ Data suggests that health home implementation has not improved CVD risk factor control among health home participants with SMI.³¹

Our research on health home implementation, including interviews and surveys with >80 health home leaders and >650 front-line providers and staff, suggests that lack of standardized systems and processes for tracking and coordinating evidence-based CVD risk factor care is a key barrier to achieving such care in health home programs.³⁴ Systems for tracking and ensuring receipt of evidence-based guidelines, e.g. hemoglobin A1C (HbA1C) monitoring among consumers with diabetes, are lacking, as are standard protocols for delivering or coordinating appropriate care with primary care providers when consumers’ CVD risk factors are poorly controlled.³⁴ Health homes received no formal guidance on how to set up such systems.

In this pilot study guided by the Translating Evidence into Practice (TRIP) framework,⁵⁶ we will partner with 5 health home programs to test an adapted Comprehensive Unit Safety Program (CUSP) implementation strategy designed to improve delivery of the evidence-based care delivery processes, e.g. population health management and care coordination, needed to implement evidence-based CVD risk factor care in SMI health homes. CUSP is a scalable implementation strategy that includes provider training and implementation of a team-based quality improvement process. CUSP is endorsed by AHRQ⁵⁷ and leads to significant improvements in inpatient safety;³⁷⁻⁴¹ CUSP is more recently being applied to outpatient quality improvement.⁴²⁻⁴⁵ Our study is the first to adapt CUSP for the community mental health setting.

4. Study Procedures

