- a. Study design, including the sequence and timing of study procedures (distinguish research procedures from those that are part of routine care).
- b. Study duration and number of study visits required of research participants.

Currently this protocol is being submitted as a study where all study procedures are delivered remotely. If and when COVID-19 restrictions are lifted, we may submit a petition to have some of the study activities (e.g., training) in-person as appropriate.

Overview: We will work with 5 behavioral health home programs in Maryland. Health homes are responsible for coordinating physical health care for persons with serious mental illness and are based in community mental health programs. The project will pilot test a comprehensive unit-based safety program (CUSP) to implement evidenced-based practices to guide delivery of care for hypertension, dyslipidemia and diabetes for persons with serious mental illness in the behavioral health homes. The project will also characterize implementation processes, organizational and provider-level factors, and cardiovascular disease risk factor care and control. The health home programs are already providing care in these domains for these individuals with serious mental illness. They will not be expanding their scope of practice with this project. The evidenced-based practices (“evidence bundle”) the study team is providing training for as part of the CUSP model are based on current practice guidelines.⁵⁸⁻⁶³ CUSP is a quality improvement implementation strategy.

Study sites and participants: We plan for five community psychiatric rehabilitation programs that have health home programs to participate in the study. Participants will be health home team staff including a nurse care manager, a primary care consultant (primary care physician or nurse practitioner), and psychiatric rehabilitation program staff who work with the health home program. Other study participants will include the broader psychiatric rehabilitation program staff and primary care physicians outside the community mental health organization with whom the health home coordinates care. Persons with serious mental illness enrolled in the health home are also study participants as their data will be analyzed.

Study implementation intervention: CUSP

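### The mediation test in Section 7 does not separate change within sites from standing differences between sites, so better-organised sites could be read as CUSP working through culture

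*Combined protocol and SAP*

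**What the plan says.** Section 7a describes culture and self-efficacy as "the mechanisms through which CUSP is designed to improve delivery of evidence-based care". It sets out three analyses that matter here:

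- The first will "compare pre/post (baseline, 12 mo.) quality improvement culture and provider self-efficacy".
- The second will "evaluate the effects of CUSP (baseline, 6 mo, 12 mo) on consumer-level evidence-based care and CVD risk factor control outcomes".
- The third, on mediation, asks if the sites' scores "mediate CUSP's effects on health home enrollee outcomes by adding these variables to the multi-level models of health home enrollee outcomes".

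Section 7a does not say whether the score entered is the baseline value, the 12-month value, a time-varying value or a change. It mentions no within-site centring, site fixed effects or indirect-effect estimate, and no rule for declaring mediation. Nothing links the first analysis to the third.

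On design, Section 4 states "We will work with 5 behavioral health home programs in Maryland". The item on a control arm reads "Justification for inclusion of a placebo or non-treatment group N/A". Section 3 (Background) notes that "each site chooses their own service structure (ranging from co-location to facilitated referral to offsite primary care services".

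**The concern.** With no concurrent control, CUSP's effect is visible only as change over time inside each of five sites. Mediation of that effect must therefore run through change as well: when a site's culture rises, do its enrollees' outcomes rise with it?

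A site's culture level also carries a second relation: whether sites with better culture have better outcomes throughout. That relation can exist before CUSP starts, and service structure, which differs by site, is one possible source. It says nothing about how CUSP works.

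At stake is the study's statement on mechanism, which would inform the wider model that the pilot is meant to support. A positive coefficient could be reported as CUSP acting through culture when the change under CUSP contributed nothing.

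**Working it through.** The plan states no sample size, alpha or effect size, so there is no figure of its own to reproduce. The check has four steps.

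**1. What the added coefficient estimates.** Write the score of site j at time t as its mean over the two waves plus the deviation from that mean.

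- *Site-constant score (for example baseline).* The deviation is zero, so the coefficient is purely between-site. With balanced data the time (CUSP) coefficient does not move when the score is added; the largest change found numerically was about 2e-15.
- *Time-varying score.* The coefficient is a weighted average of the within-site and between-site slopes. A random site intercept does not remove the between-site part, because the intercept is assumed uncorrelated with the score.

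**2. Error when there is no mediation.** From the documents: 5 sites, mediators at baseline and 12 months, about 30 culture respondents per site, about 200 enrollees per site. Everything else is assumed:

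- logit-scale outcome, 100 eligible enrollees per site and wave at 50% control, so cell variance = 1/(100 × 0.5 × 0.5) = 0.04
- site outcome SD 0.4 log-odds; site culture SD 0.3 points
- culture standard error = 0.6/√30 = 0.11
- culture shift 0.3 (SD 0.15 between sites)
- outcome trend 0.4 log-odds, the same at every site and not caused by culture
- within-site effect of culture exactly 0
- one mediator, REML random site intercept, Wald test at two-sided 5%

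| Correlation of standing culture with standing outcome | Normal critical value | t(3) critical value |
|---|---|---|
| 0 | about 11% | about 2% |
| 0.5 | about 20% | about 7% |
| 0.8 | about 40% | about 18% |

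The normal-value excess at correlation 0 is the few-sites effect alone. The rise below it is the between-site contamination, and t(3) does not remove that rise.

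A second model (continuous outcome, site ICC 0.05, culture unchanged by CUSP) gives the following at correlations 0, 0.5 and 0.8:

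- time-varying score: 9.2%, 18.6%, 38.0% (t(3): 1.9%, 5.8%, 19.0%)
- site-constant score: 13.8%, 26.8%, 56.8% (t(3): 4.1%, 10.4%, 32.0%)

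**3. Two possible safeguards.**

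- *Also requiring a significant pre/post culture change* (second model, time-varying score, normal critical value). If culture does not move, false mediation is 0.7% to 4.2% over correlations 0 to 0.95. If culture rises by 0.3, as the study hopes, it is 9.9%, 15.2% and 29.6% at correlations 0, 0.5 and 0.8.
- *Judging mediation by shrinkage of the time effect.* In balanced data, shrinkage = added coefficient × mean culture change. In the first model at correlation 0.8 the time effect falls from 0.40 to about 0.24. The implied coefficient is (0.40 − 0.24)/0.3 = 0.53 log-odds per point, although the true within-site effect is 0. The between-site slope, ignoring measurement error, is 0.8 × 0.4/0.3 = 1.07, so about half of it leaks into the supposed mediation.

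**4. The split.** Enter site mean and within-site deviation, and test only the deviation. With a common trend, false mediation is 3.5% to 6.0% in the first model and 4.2% to 5.8% in the second, whatever the correlation. If sites improve at different rates for reasons unrelated to culture, normal critical values no longer hold: about 10-12% at trend SD 0.2 log-odds and about 25% at 0.4.

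The within-site test rests on five site changes. Regressing them on one mediator's change leaves 5 − 2 = 3 degrees of freedom, or 5 − 3 = 2 with both mediators. Significance then needs a correlation (partial, with both) above 0.878 or 0.950 in absolute value. Using 1.96 on such a statistic gives a true error of 14.5% or 18.9%.

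**The case against.** The best defence is that the plan does not commit to a level. The same paragraph presents culture and self-efficacy through their pre/post comparison, so a change score is an open reading, and that form would escape the problem. This stands as a limit: the fault is that the form is unspecified and its plain reading is confounded.

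A reader might go further and infer that the planned test only asks whether culture and outcome are related across sites. That is exact only for a site-constant score. A time-varying score gives a blend, and the text does not say which is meant.

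The plan also gives no rejection rule, so the percentages belong to an assumed Wald test. Under a shrinkage rule a site-constant score could not show mediation at all, true or false. A time-varying score would still mislead, as step 3 shows.

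The correlations are assumed too. Section 3 says that service structure varies, not that it tracks culture.

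Finally, this is a pilot. Mediation is not among the Aim 2 hypotheses, and power is poor in either form: about 16% for the added score and 13% for the split, for a true within-site effect of 1 log-odds per point (normal critical values, culture shift 0.4 with SD 0.15, no other trend). That limits the consequence and argues for an exploratory label. It does not justify leaving the two relations mixed.

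**Conclusion.** The concern holds in a qualified form. As written, Section 7a allows a mediation result driven partly by standing differences between sites, or wholly so if the score is constant within site. Nothing in the documents prevents it.

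The error rates in step 2 show direction and range. They do not predict this trial, because they depend on assumed variances, an assumed correlation, a single mediator and a common trend across sites.

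A reader might also infer that splitting the score is enough to hold error at 5%. That is so only if all five sites share the same trend, and the documents give no ground for assuming it. The split removes the between-site contamination; small-sample inference is needed as well.

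**What to change.** In Section 7a, replace the instruction to add the variables with wording such as:

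> Each site's culture and self-efficacy score will be split into the site's mean over baseline and 12 months and the deviation from that mean. Both parts will enter the model with time. Only the within-site coefficient, together with the pre/post change in that mediator, will be read as evidence on mediation. The site-mean coefficient will be reported as a between-site association. Inference will use small-sample methods based on the five site changes. The mediation analysis is exploratory.

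Site fixed effects would give the same protection against between-site differences. The text should also say how the 6-month outcomes are handled, since the mediators have no 6-month value.

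The cost is a few sentences and two derived variables per mediator, from data already to be collected. The downside is that five sites give an imprecise within-site estimate, and small-sample critical values widen its interval further. The mediation result will look weaker than the pooled coefficient would.
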